7.2 Screening / Baseline

The following tests and examinations must be performed prior to the procedure to verify eligibility and to collect baseline study data:

- Relevant medical history and patient demographic information, including STS Risk Score and EuroSCORE II risk evaluations
- Physical examination including ischemic / anginal status (CCS or silent ischemia), NYHA functional capacity, heart rate, blood pressure, height, and weight
- Frailty assessment with the Clinical Frailty Scale
- Concomitant medication documentation
- Review of the study eligibility criteria (inclusion and exclusion). NOTE: If the full screening/baseline review of eligibility criteria is conducted before the day of enrollment, the following repeat review of selected eligibility criteria should be performed on the day of enrollment and randomization (§6.2.1) to confirm study eligibility, using the most recent available laboratory values and clinical assessments:
 - Ensure that the subject has not had symptoms or chemistry results indicating acute myocardial infarction (§6.1.2.1.5)
 - Ensure that the most recent eGFR remains ≥ 30 (§6.1.2.1.10)
 - Ensure that there are no signs of cardiogenic shock (§6.1.2.1.13)
 - Review the planned approach for TAVI, as certain approaches will make the subject ineligible for the study (§6.1.2.1.1, §6.1.2.1.2)
- Routine laboratory tests including:
 - Hematology - hemoglobin, hematocrit, platelet count, white blood cell count within 14 days prior to the procedure

- Chemistry - creatinine, ALT/serum glutamic-pyruvic transaminase (SGPT), and AST/serum glutamic-oxaloacetic acid transaminase (SGOT) within 14 days prior to the procedure,
- Cardiac enzymes (CK), isoenzymes CK-MB or troponins should be obtained when clinically indicated (for example if there is a suspected ischemic event).
- Female patients of childbearing potential must also have a pregnancy test within 14 days prior to the procedure.
- At the investigator's discretion and according to site standard practice, subjects requiring warfarin therapy may undergo a pre-procedure Coagulation Panel including prothrombin time, partial thromboplastin time (PTT) and International Normalized Ratio (INR) to ensure compliance with the concomitant therapy recommendations (§7.3).
- A 12-lead electrocardiogram. An ECG performed within 30 days prior to the procedure may be used as the baseline ECG provided there have been no signs or symptoms of myocardial ischemia between the time of the ECG and enrollment (in which case the ECG should be performed within 24 hours prior to enrollment).
- CT imaging (standard and contrast-enhanced angiography preferred) of the left heart, aorta, great vessels, and peripheral access vessels performed up to 1 year prior to the procedure should be submitted for review.
- NIH Stroke Scale (NIHSS) up to 14 days prior to procedure. Neurologic status evaluation using the NIH stroke scale shall also be performed 2-5 days post-procedure and during each follow-up assessment. The examination must be performed by a neurologist, or a clinical designee (e.g. neurology fellow).
- Modified Rankin Scale (mRS) up to 14 days prior to procedure. The mRS will also be performed 2-5 days post-procedure and during each follow-up assessment. The assessment must be performed by a neurologist or a clinical designee (e.g. neurology fellow).
- A full neurological evaluation should be performed by a neurologist in all patients in whom a stroke or TIA is suspected on the basis of the NIHSS, mRS, or other signs or symptoms.
- A neuropsychological test battery (§16.7) will be administered up to 30 days prior to procedure by a qualified individual, and will be re-administered 2-5 days post-procedure and at 30 and 90 days. The test battery includes: (Phase I only)
 - Montreal Cognitive Assessment (MoCA) - A cognitive screening instrument that includes tasks that assess attention and concentration, executive functions, memory, language, visuoconstructional abilities, abstraction, calculations, and orientation. It takes approximately 10 minutes to administer and is available in several languages.
 - Repeatable Battery for the Assessment of Neuropsychological Status (RBANS) - A comprehensive, but brief, neuropsychological battery that includes assessment of immediate memory, visuospatial/constructional abilities, language, attention, and delayed memory. The RBANS is available in many different languages and typically takes less than 30 minutes to administer. Alternate forms of the tests are used for repeat testing.

- Trail Making Test Parts A & B. These tests evaluate attention, psychomotor speed, and mental flexibility. In Part A, the subject connects 25 encircled numbers in ascending order as quickly as possible. In Part B, the subject connects encircled numbers and letters in ascending order, alternating between the two (i.e., 1-A-2-B-etc.). The total administration time is less than 10 minutes.
- The Short Form 36 Health Survey (SF-36v2) will be administered up to 30 days prior to procedure, and will be re-administered at 30. The SF-36 is a 36-item questionnaire that measures health-related quality of life across 8 physical and mental domains. It is available in many different languages and takes approximately 10 minutes to administer. When administered during a visit that includes other assessments, the SF-36 should be performed first (Phase I only).

7.3 Concomitant Therapies

Selection and dosing of procedural and post-procedural concomitant therapies, including antiplatelet and anticoagulant therapies, will be performed according to physician standard practice, in accordance with local standards of care and published guidelines. Each site is encouraged to commit to a consistent antiplatelet regimen to be applied to all subjects enrolled in the trial, independent of treatment group.

The investigators recommend (but do not require) that all subjects receive the medication regimen listed below (Table 8). All medications administered should be recorded in the patient's medical record and the CRF.

Table 8: Concomitant Medications

Timing	Medication	Recommended Doses
Prior to Procedure	IV Heparin or low molecular weight heparin or bivalirudin	Per routine hospital practice
During Procedure	IV Heparin or low molecular weight heparin or bivalirudin	Per routine hospital practice. It is recommended to maintain an ACT > 250 seconds. [†]
Post Procedure*	Acetylsalicylic acid (ASA)	75-100 mg QD indefinitely
	Clopidogrel	75 mg QD for a minimum of 6 months or longer based on local guidelines.

[†]Peak and nadir intraprocedural ACT measurements must be recorded in the CRF for all subjects.

***Note for patients receiving warfarin therapy:**

- *If the patient is on warfarin therapy prior to the procedure, the following is recommended:*
 - *Discontinue warfarin three days prior to the procedure*
 - *Confirm that the INR is <1.8 prior to the procedure*
 - *ASA 75-100 mg or clopidogrel 75 mg for 3 days prior to the procedure*
- *If the patient is on warfarin therapy post-procedure, it is recommended that the patient is prescribed either daily aspirin (75-100 mg) or daily clopidogrel (75 mg).*

Minimum recommended maintenance dosages can be higher based on physician's discretion.

7.4 TAVI Procedure

TAVI will be performed according to standard institutional practice under local or general anesthesia and via the transfemoral approach at the discretion of the investigator.

In subjects in the Intervention or Roll-in Groups, the TriGuard HDH or TriGUARD 3 device will be advanced and deployed across the aortic arch to cover the ostia of the 3 major vessel takeoffs (innominate, left carotid and subclavian arteries) at the initiation of the TAVI procedure and withdrawn at the completion of the procedure. Please refer to the TriGuard HDH or TriGUARD 3 Instructions For Use for additional information.

Device coverage and positioning must be verified by fluoroscopy (a steep left anterior oblique [LAO] view is recommended), with particular attention paid to 1.) Device coverage after initial deployment, 2.) Device positioning after final deployment of the first prosthetic valve, and 3.) Device positioning after the procedure is complete (i.e., after any additional post-dilatation or additional valve implantations have been completed, and the TAVR delivery system has been removed). All imaging should be forwarded to the Angiographic Core Laboratory for analysis. For additional details, please refer to the Angiographic Imaging Acquisition Guidelines (§16.8).

7.5 Post-procedure Follow-up

The procedure is considered complete once the last guiding catheter has been removed from the patient and the patient is off the table. Thereafter, if a guiding catheter is re-introduced, this is considered a repeat intervention, which must be documented.

The post-procedure follow up will consist of:

- Physical examination including ischemic / anginal status (CCS or silent ischemia), heart rate, and blood pressure
- Documentation of any adverse events/ serious adverse events occurring since the point of enrollment
- Current concomitant medications documentation, including antiplatelet and anticoagulant therapy
- Routine laboratory tests including:
 - Hematology - hemoglobin, hematocrit, platelet count, white blood cell count
 - Chemistry - creatinine. Serum creatinine should be measured within 48 hours post-procedure in all subjects. Subjects with elevated serum creatinine ($\geq 1.5 \times$ baseline OR > 0.3 mg/dL [> 26.4 mmol/L]) should have continued assessments to 7 days post-procedure or until discharge (whichever occurs first) to assess acute kidney injury.
 - Cardiac enzymes: CK/CKMB or Troponin (preferably CKMB isoenzyme) will be measured when clinically indicated. If cardiac biomarkers are elevated, they should be repeated per local standard of care.
- A 12-lead ECG, to be completed within 24 hours post-procedure or prior to hospital discharge (whichever occurs first)
- If echocardiography (transthoracic or transesophageal) was performed after TAVR prosthesis implantation as part of the standard of care, the relevant parameters (including mean aortic valve gradient, peak velocity, and degree of prosthetic aortic

valve regurgitation) must be captured on the eCRF for evaluation in-hospital TAVI device success (§□)

- Diffusion-weighted MRI of the brain 2 to 5 days (≥ 48 to < 144 hours) post-procedure
- NIH Stroke Scale (NIHSS). Neurologic status evaluation using the NIH stroke scale shall be performed 2 to 5 days (≥ 48 to < 144 hours) post-procedure and during each follow-up assessment. The examination must be performed by a neurologist or a clinical designee (e.g. neurology fellow).
- Modified Rankin Scale (mRS) shall be performed 2 to 5 days (≥ 48 to < 144 hours) post-procedure and during each follow-up assessment. The assessment must be performed by a neurologist or a clinical designee (e.g. neurology fellow).
- A full neurological evaluation should be performed by a neurologist in all patients in whom a stroke or TIA is suspected on the basis of the NIHSS, mRS, or other signs or symptoms.
- A neuropsychological test battery (§16.7) will be administered 2 to 5 days (≥ 48 to < 144 hours) post-procedure by a qualified individual. The test battery includes: (Phase I only).
 - Montreal Cognitive Assessment (MoCA)
 - Repeatable Battery for the Assessment of Neuropsychological Status (RBANS)
 - Trail Making Test Parts A and B

Prior to hospital discharge, research staff should also review the follow-up requirements with the subject to help ensure that the patient returns to the clinic for the one-month follow-up visit. Telephone numbers should be obtained from the patient to ensure the ability to contact him or her at the required time. These phone numbers should include all home numbers, work numbers and primary physician numbers. A phone number of a relative or friend should also be requested.

Note: All clinically significant adverse events should be carefully documented by the research staff using the adverse event data forms. Any clinically-indicated neuroimaging should be forwarded to the MRI Core Laboratory.

7.6 One-month Follow-up (Clinic Visit)

All subjects will return to the clinic at 30 days (± 7 days) post-procedure for a clinical evaluation.

The 30 day follow-up visit will consist of the following assessments:

- Physical examination
- Documentation of any adverse events/ serious adverse events occurring since the previous evaluation
- Current concomitant medication documentation, including antiplatelet and anticoagulant therapy
- NIH Stroke Scale (NIHSS): Neurologic status evaluation using the NIH stroke scale must be performed by a neurologist or a clinical designee (e.g. neurology fellow).
- Modified Rankin Scale (mRS) must be performed by a neurologist or a clinical designee (e.g. neurology fellow).

- A full neurological evaluation should be performed by a neurologist in all patients in whom a stroke or TIA is suspected on the basis of the NIHSS, mRS, or other signs or symptoms.
- A neuropsychological test battery (§16.7), to be administered by a qualified individual. The test battery includes: (Phase I only)
 - Montreal Cognitive Assessment (MoCA)
 - Repeatable Battery for the Assessment of Neuropsychological Status (RBANS)
 - Trail Making Test Parts A and B
- The Short Form 36 Health Survey (SF-36) (Phase I only)

Prior to concluding the visit, research staff should also review the follow-up requirements with the subject to help ensure that the patient can be contacted by telephone at the three-month follow-up time point.

Note: All clinically significant adverse events should be carefully documented by the research staff using the adverse event data forms. Any clinically-indicated neuroimaging should be forwarded to the MRI Core Laboratory.

7.7 Three-month Follow-up

7.7.1 Phase I:

All subjects in Phase I were expected to return to the clinic at 90 days (\pm 14 days) post-procedure for a clinical evaluation.

The 90 day follow-up visit consisted of the following assessments:

- Physical examination including ischemic / anginal status (CCS or silent ischemia), heart rate, and blood pressure
- Frailty assessment with the Clinical Frailty Scale
- Documentation of any adverse events/ serious adverse events occurring since the previous evaluation
- Current concomitant medication documentation, including antiplatelet and anticoagulant therapy
- NIH Stroke Scale (NIHSS): Neurologic status evaluation using the NIH stroke scale must be performed by a neurologist or a clinical designee (e.g. neurology fellow).
- Modified Rankin Scale (mRS) must be performed by a neurologist or a clinical designee (e.g. neurology fellow).
- A full neurological evaluation should be performed by a neurologist in all patients in whom a stroke or TIA is suspected on the basis of the NIHSS, mRS, or other signs or symptoms.
- A neuropsychological test battery (§16.7), to be administered by a qualified individual. The test battery includes:
 - Montreal Cognitive Assessment (MoCA)
 - Repeatable Battery for the Assessment of Neuropsychological Status (RBANS)
 - Trail Making Test Parts A and B

- The Short Form 36 Health Survey (SF-36)

Note: All clinically significant adverse events should be carefully documented by the research staff using the adverse event data forms. Any clinically-indicated neuroimaging should be forwarded to the MRI Core Laboratory.

7.7.2 Phase II:

In Phase II, a telephone contact at 90 days (\pm 14 days) post-procedure will establish:

- Mortality
- Stroke

If death or stroke is reported, source documentation will be requested from treating facility to enable CEC adjudication of cause of death (cardiovascular [subclassified and neurologic-event related] or non-cardiovascular) and stroke classification according to the protocol-specified definitions.

8.0 Device Accountability

The Site Principal Investigator is responsible for device accountability at his/her trial site and must maintain associated trial records according to 21 CFR Part 812.140 (§15.5.2). The investigator may assign the responsibility for device accountability to an appropriate study staff member, but remains the final responsible person.

The investigator will maintain device use/disposition records that document device delivery to the trial site, the inventory at the site, administration to each patient as well as any device that was opened but not used. These records must include dates, quantities, batch/serial numbers, expiration dates, and the unique code numbers assigned to the trial patients. The investigator must maintain records that adequately document which device was used (or exposed to the circulation) of each subject and any device malfunctions.

At the trial closeout visit, the Investigator must return to the Sponsor any unused devices and a copy of the completed device inventory. The Investigator's copy of the device reconciliation records must document all device usage (including devices that were opened but not used) and any unused devices that have been returned to the sponsor.

9.0 Adverse Events, Serious Adverse Events, and End-points Potentially Meeting End-point Criteria

In this study, patients should be encouraged to report adverse events (AEs) spontaneously or in response to general, non-directed questioning. Any time during the study, the patient may volunteer information that resembles an adverse event (AE). If it is determined that a clinically significant AE has occurred, the investigator should obtain all the information required to complete the AE CRFs. Non-clinically-significant adverse events will not be required post discharge from the initial study procedure.

9.1 Adverse Events (AE)

An adverse event is any untoward medical occurrence, unintended disease or injury or any untoward clinical signs (including an abnormal laboratory finding) in subjects, users or other persons, whether or not related to the study device.

NOTE: This definition includes events related to the study device or to the procedures involved, but does not imply that there is a relationship between the adverse event and the study device.

Pre-Existing Conditions:

Pre-existing medical conditions or a repeat of symptoms reported prior to the TAVR procedure will not be recorded as an AE. Pre-existing conditions that worsen during a study are to be considered adverse events. For users or other persons, this classification is restricted to events related to the study device.

9.2 Serious Adverse Events (SAE)

A serious adverse event is an adverse event that:

1. Led to a death
2. Led to a serious deterioration in the health of the subject that:
 - a. Resulted in a life-threatening illness or injury
 - b. Resulted in a permanent impairment of a body structure or a body function
 - c. Required in-patient hospitalization or prolongation of existing hospitalization
 - d. Resulted in medical or surgical intervention to prevent life-threatening illness or injury or permanent impairment to body structure or a body function.
3. Led to fetal distress, fetal death or a congenital abnormality or birth defect.

9.3 Adverse Device Effect (ADE)

An adverse device effect is an adverse event related to the use of a medical device. This includes:

- Any adverse event resulting from insufficiencies or inadequacies in the Instructions for Use, the deployment, the implantation, the installation, the operation, or any malfunction of the medical device
- Any event that is a result of a use error or intentional misuse

9.4 Serious Adverse Device Effect (SADE)

A serious adverse device effect is an adverse device effect that has resulted in any of the consequences characteristic of a serious adverse event.

9.5 Unanticipated Adverse Device Effect (UADE)

An unanticipated adverse device effect is any serious adverse effect on the health or safety or any life-threatening problem or death caused by, or associated with, a device, if that effect, problem, or death was not previously identified in nature, severity or degree of incidence in the investigational plan or application (including a supplementary plan or application), or any other unanticipated serious problem associated with a device that relates to the rights, safety or welfare of subjects.

NOTE: An anticipated serious adverse device effect (ASADE) is a serious adverse device effect which by its nature, incidence, severity, or outcome has been identified in the investigational plan or application (including a supplementary plan or application).

9.6 Device Deficiencies, Malfunctions, and Use Error

Investigators are instructed to report all possible device deficiencies, malfunctions, misuse or use error observed during the course of the trial. These incidents will be documented in the case report form provided as follows:

- **Device deficiency:** Inadequacy of a medical device related to its identity, quality, durability, reliability, safety or performance. NOTE: Device deficiencies include malfunction, use error, and inadequate labeling. They may or may not affect device performance or lead to an adverse event.
- **Device malfunction:** Failure of an investigational medical device to perform in accordance with its intended purpose when used in accordance with the Instructions for Use or protocol. NOTE: A device malfunction occurs when the device is used in compliance with the Instructions for Use, but does not perform as described in the Instructions for Use.
- **Use error:** Act or omission of an act that results in a different medical device response than intended by the manufacturer or expected by the user. NOTE 1: Use error includes slips, lapses and mistakes. NOTE 2: An unexpected physiological response of the patient does not itself constitute a use error.
- **Device misuse:** Any use of the investigational device by an investigator that is contradictory to the application described in the Instructions for Use will be categorized as device misuse. This is a form of Use Error.

9.7 End-points Potentially Meeting End-point Criteria

Investigators are instructed to report all cardiovascular events and all adverse events potentially meeting end-point criteria. These events will be documented in the case report form as SAEs and be assessed by the medical monitor. Events classified as potential end-points will then be sent to CEC adjudication (§11.2).

9.8 Documentation

Adverse events must be listed on the appropriate CRF. All AEs will be characterized by the following criteria:

- Intensity or Severity
- Relatedness
- Outcome
- Treatment or Action Taken

9.8.1 Intensity or Severity

The following categories of the intensity of an adverse event are to be used:

Mild	Awareness of a sign or symptom that does not interfere with the patient's usual activity or is transient, resolved without treatment and with no sequelae.
Moderate	Interferes with the patient's usual activity and/or requires symptomatic treatment.
Severe	Symptom(s) causing severe discomfort and significant impact of the patient's usual activity and requires treatment.

9.8.2 Relatedness

The investigator will use the following definitions to assess the relationship to the device:

Not related	The cause of the AE is known and the event is not related to any aspect of study participation.
Unlikely to be related	There is little or no temporal relationship to the study device and/or a more likely alternative etiology exists.
Possibly related	There is a reasonable possibility that the event may have been caused by study participation. The AE has a timely relationship to the study procedure(s); however, follows no known pattern of response , and an alternative cause seems more likely or there is significant uncertainty about the cause of the event.
Probably related	It is likely that the event was caused by study participation. The AE has a timely relationship to the study procedure(s) and follows a known pattern of response ; a potential alternative cause, however, may explain the event.
Related	A related event has a strong temporal relationship and an alternative cause is unlikely.

If the relationship between any adverse event and the use of the investigational medical device is considered to be possibly or probably related, that event will be classified as an ADE or SADE.

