9.10 Expected Adverse Events

As with any endovascular intervention, TAVI involves some risks and possible complications. The following anticipated events have been identified as possible complications of TAVI procedures:

- Acute cardiovascular surgery (need for)
- Acute coronary artery occlusion
- Acute myocardial infarction
- Acute neurological events such as stroke, transient ischemic attack (TIA), and encephalopathy
- Allergic reaction to contrast, antiplatelet therapy or device component materials
- Angina pectoris
- Anesthesia reactions
- Aneurysm or pseudoaneurysm
- Arteriovenous fistula
- Ascending or descending aorta trauma
- Atrial or ventricular arrhythmias or fibrillation or sustained heart palpitations requiring therapy
- Bleeding complications such as hematoma and hemorrhage
- Blood loss requiring transfusion
- Bowel ischemia
- Coronary artery or other vascular injury, dissection, or perforation (which may require repair)
- Embolism (air, tissue, device, or thrombus)
- Fever
- Femoral nerve damage
- Hemodynamic changes
- Hypertension or hypotension (sustained requiring therapy)
- Infection, including endocarditis and septicemia
- Pain (at the femoral puncture site, abdominal, back, or other)
- Percutaneous coronary intervention (need for)
- Peripheral ischemia, peripheral nerve damage

- Pulmonary edema
- Pyrogenic reaction
- Renal complications, injury, or failure
- Unstable angina
- Vascular complications which may require vessel repair
- Vessel spasm (sustained, not responding to therapy)

In addition to the risks listed above, the potential risks specifically associated with the TriGuard HDH or TriGUARD 3 procedure include, but may not be limited to, the following:

- Dissection of the innominate artery by improper manipulations, disruption or migration of the TriGuard HDH CEPD filter due to passage of other instrumentation, e.g.: balloon, stent, catheter, wire
- Blue toe syndrome or blue discoloration of a toe
- Femoral bleeding at the access site
- Local trauma to the aortic wall due to device migration

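### The relatedness grades in section 9.8.2 are meant to judge the device but are mostly worded against study participation, so a complication of TAVI alone may be labelled an adverse device effect

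*Combined protocol and SAP*

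**What the plan says.** Section 9.8.2 opens by stating its purpose: "The investigator will use the following definitions to assess the relationship to the device". Five grades follow.

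- *Not related*: a known cause, with no link of any kind to being in the study.
- *Unlikely to be related*, the one grade that names the device: "There is little or no temporal relationship to the study device and/or a more likely alternative etiology exists".
- *Possibly related*: a reasonable possibility that participation in the study was the cause, with timing that fits the study procedure(s), no known response pattern, and either a likelier alternative cause or real uncertainty.
- *Probably related*: likely "caused by study participation. The AE has a timely relationship to the study procedure(s) and follows a known pattern of response", although another cause might explain the event.
- *Related*: "A related event has a strong temporal relationship and an alternative cause is unlikely".

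The section closes by making an event an ADE or SADE when its relationship to use of the device is graded possibly or probably related. *Related* is not mentioned in that sentence. Section 9.3 likewise defines an ADE by use of a medical device.

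Section 9.8 asks for one relatedness characteristic per event. It makes no separate provision for relationship to TAVI.

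**The concern.** A relatedness scale needs one referent. Here the introduction and the ADE/SADE rule refer to the device, while most of the grades refer to being in the study or undergoing its procedure. In a trial where every subject has TAVI, these are different questions.

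The difference is practical. Under section 12.3.3 the device is introduced through the contralateral femoral artery, so a device subject has access sites for both the valve and the device. Section 9.10 lists bleeding and vascular complications among the risks of TAVI. It then says that "the potential risks specifically associated with the TriGuard HDH or TriGUARD 3 procedure include" femoral bleeding at the access site, among others. A site may know which access bled, but the single scale gives it no unambiguous way to say so.

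At stake is the meaning of the investigator's ADE and SADE labels, and of the only relatedness grade available for events that the CEC does not review.

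**Working it through.** No formula applies. Section 9.8.2 states no figure, and nothing here depends on alpha, power, a rate or a margin. The check is of the text.

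**Step 1. What each grade refers to.**

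| Grade | Study participation | Study procedure(s) | Device |
|---|---|---|---|
| Not related | yes | no | no |
| Unlikely | no | no | yes |
| Possibly | yes | yes | no |
| Probably | yes | yes | no |
| Related | no | no | no |

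Three grades refer to participation, and two of these also to the procedure. One refers to the device and one has no stated referent: 3 + 1 + 1 = 5.

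**Step 2. Whether those terms include TAVI.** Section 10.1 describes most risks of taking part in the trial as much the same as those of TAVI outside it, so participation includes TAVI risk. Section 9.0, repeated in section 9.9.1, says: "Non-clinically-significant adverse events will not be required post discharge from the initial study procedure". That rule applies to all subjects, controls included, so the study procedure there appears to be the index procedure and not device insertion alone.

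**Step 3. One event through the scale.** Take a bleed from the TAVI access site in a device subject, with no contribution from the device.

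- *Not related* is closed: the cause is known, but it is an aspect of participation.
- *Probably* is met: the event was likely caused by participation, fits the procedure in time and follows a known pattern.
- *Unlikely* is also met through its second limb: relative to the device, TAVI is the more likely cause.

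Two careful investigators can therefore grade the same event differently. One grade leads to an ADE or SADE label and the other does not.

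**Step 4. Two further faults in the same section.** *Possibly* allows an alternative cause that seems more likely. *Unlikely* requires little or no temporal relationship, or a more likely alternative cause, or both. An event with a likelier alternative can thus fit either grade. The ADE/SADE sentence also omits *Related*, so read literally the strongest grade does not trigger the label.

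**Step 5. Where the investigator's grade is used.**

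- ADE and SADE labelling (sections 9.3, 9.4 and 9.8.2): used directly.
- Primary safety endpoint (section 12.4.2): not used. Composite events in the intervention group are tested against 34.4% whatever their cause.
- Secondary safety rates (section 5.4.2.1.2): not used. Overall rates are reported by treatment group.
- Relatedness table (section 12.4.9): not used. It takes the CEC's judgement.
- Events outside CEC scope: it is the only grade. Section 11.2 limits the CEC to cardiovascular events and potential endpoint events, with potential endpoints screened first by the medical monitor.

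**The case against.** The strongest reply is that the operative rule is sound. The ADE/SADE sentence and section 9.3 both turn on use of the device, and *Unlikely* gives a proper home to a complication of TAVI alone. This stands in part: such an event may be misclassified but need not be. It does not remove the defect, because the grade feeding the rule can be reached on participation alone.

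Reporting also depends less on the grade than it might seem. Section 9.9.2 recommends notifying the sponsor of every serious event within 3 working days, and treats cardiovascular and potential endpoint events as serious. The 48-hour SADE rule there concerns EU sites in Phase I and applies only where local or national rules require it; Phase II is conducted in the United States. The sponsor evaluates serious events for unanticipated status. Over-inclusive grading would add reports, not suppress them.

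Three stronger conclusions might be inferred, and the documents do not support them.

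- *A true device signal would be hidden.* Harm would appear in by-arm rates and in the primary safety test, neither of which uses relatedness. Section 12.4.9 lists no table of ADE or SADE counts.
- *Control-arm complications would become device effects.* A control could receive a misleading grade, but with no device used the ADE rule cannot be met.
- *The expected 25% composite rate sizes the problem.* Section 11.2 puts those components within CEC scope, so that rate does not measure the residual problem. It would also require assuming that nearly all such events are graded literally.

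CEC review reduces the problem without fully resolving it. Its category combines the investigational device and the investigational procedure, and Appendix I does not define the latter.

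**Conclusion.** The concern holds in a limited form. The scale's stated purpose and its wording disagree, and a complication of TAVI alone can meet two grades with opposite consequences for ADE/SADE status. The consequence is possible misclassification in investigator-graded ADE/SADE data and in events outside CEC scope. The primary safety endpoint, by-arm rates, CEC-based relatedness table, sample size, power and alpha are unaffected.

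This rests on reading participation and study procedure as sections 10.1, 9.0 and 9.9.1 use them, and on the form following section 9.8.2; the case report form is not among the documents. They do not say how many events would fall outside CEC scope, so no count can be given. The wording should be corrected, but it does not threaten the trial's main safety conclusions.

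**What to change.** In section 9.8.2:

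1. Word all five grades against one referent: the investigational device or its insertion, use or removal.
2. Base ADE and SADE status on that grade, and add *Related* to the sentence that assigns it.
3. Redraw *Possibly* and *Unlikely* so that an event with a likelier alternative cause fits only one of them.
4. Mark the device item not applicable for control subjects.

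A separate item for relationship to TAVI on the adverse event form would help sites record what they know, but it is optional once the device grade has a clear referent.

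The cost is wording in one section and at most one item on the electronic form. No new data source is needed.
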